**POSTOPERATIVE GLYCAEMIC CONTROL AND THE SURGICAL SITE INFECTION
INCIDENCE AMONG LIVER TRANSPLANTATION RECIPIENTS: RANDOMIZED
CLINICAL TRIAL**

Date: March 13th, 2018.

Version: 1

Author:

[name],

Sao Paulo Registered Nurses Board: Number 265.476

RN, MSc, PhD Candidate at University of São Paulo School of Nursing.

Graduate Program in Adult Health Nursing.

[name].

E-mail: [contact]

[contact]

**POSTOPERATIVE GLYCAEMIC CONTROL AND THE SURGICAL SITE INFECTION
INCIDENCE AMONG LIVER TRANSPLANTATION RECIPIENTS: RANDOMIZED
CLINICAL TRIAL**

ABSTRACT

Context: The hyperglycemia is an important independent risk factor for the Surgical Site Infection (SSI) development among liver transplantation recipients. **Objective:** To evaluate the effects of an intensive postoperative protocol of blood glucose management on the surgical site infection incidence among liver transplantation recipients. **Material and methods:** It is an open-label clinical trial that will be randomized into 2 groups of blood glucose (BG) control: patients will undergo BG control regular in the facility chosen to research development (BG targeted 130-180 mg/dL) and the second one will undergo intensive BG control (BG targeted 80 - 130 mg/dL) until patients are eating at least 50% of a full liquid diet or receiving bolus tube feedings. A computer program will be employed to generate the randomized schedule that will be put into sequentially numbered opaque sealed envelopes by an external expert to research. A finger prick device will be used to measure the blood glucose. A blinded adjudication committee to analyse the primary endpoint SSI will adopt the SSI criteria given by the Centers for Disease Control and Prevention. The research proposal will be registered on ClinicalTrials.gov database. Central tendency and dispersion measures, Pearson's χ^2 test, Fisher's Exact Test, Mann-Whitney, Wilcoxon-Mann-Whitney and survival analysis by Kaplan-Meier estimated and Log-rank test will be used for data analyses. **Expected outcomes:** The results of the study should contribute to establishing better clinical practices on glycemic control in the liver transplantation recipient's postoperative period aiming to reduce SSI incidence and its associated morbidity and mortality.

Descriptors: Glycemia. Surgical Wound Infection. Liver Transplantation. Perioperative Nursing.

1 INTRODUCTION

The Surgical Site Infections (SSI's) are the most frequent healthcare-associated infections and are an important infectious complication in the postoperative period among liver transplantation (LT) recipients ⁽¹⁻³⁾. SSI incidence among LT recipients, whose allografts were from deceased donors, varied from 9.6% to 35.5% according to a recent literature review⁽⁴⁾. In general surgical procedures, SSI increases the length of stay, morbidity and healthcare costs. Besides that, among LT recipients SSI can raise the risks of the allografts dysfunctions, acute rejections and as a consequence a reduction in the recipient's survival⁽⁵⁻⁷⁾.

There are several risk factors for SSI among LT recipients. There is a relationship among supply sterilization quality, the characteristics of surgical procedure, the operation room environment as well as the allograft's and recipient's conditions and SSI occurrence⁽⁸⁻¹²⁾. In regard to LT recipients, results from previous research highlighted hyperglycemia as an important independent predictor of SSI. Furthermore, regarding this population, it is known from observational studies that LT recipients affected by hyperglycemia are exposed, approximately, to three times the risk of SSI comparatively to LT recipients not exposed⁽¹³⁻¹⁶⁾.

The concern about maintaining normoglycaemia in acute care facilities is not recent; several studies have been done including on clinical and surgical patients from some medical specialities showing the morbidity and mortality reduction throughout the adoption of strict glycaemic control protocols ⁽¹⁷⁻¹⁹⁾.

However, among critical surgical patients the LT recipients are highlighted; since they are exposed to impairment in blood glucose metabolism in the perioperative period as a consequence of an intraoperative acute stress state, blood loss and transfusions, the reperfusion phase, use of glucocorticoids and catecholamines^(20, 21).

Results from previous studies pointed the hyperglycaemia among LT recipient as a frequent complication, 94% of them presented it at least once in the transplantation's postoperative period^(22, 23).

The high blood glucose levels can produce electrolyte and acid-base disturbances besides altered plasmatic distribution of sodium⁽²⁴⁾. There are impairments to the white blood cells activities, such as reduction in the adherence, chemotaxis, phagocytosis and superoxide formation. Lymphocytes apoptosis combined with T-cell activities suppression besides attenuation of immunoglobulin's work as a consequence of glycosylation^(25, 26).

In spite of evidence from laboratory studies that indicate remarkable impairments caused by hyperglycemia in immune model animals immunologic system, uncertainties remain to evaluate the glycaemic control as a strategy for SSI prevention. Analysing the guidelines to prevent SSI published by World Health Organization⁽²⁷⁾, Centers for Disease Control and Prevention (United States of America)⁽¹⁾, National Institute for Health and Care Excellence (United Kingdom)⁽²⁸⁾, Society for Healthcare Epidemiology of America (United States of America)⁽²⁹⁾ and Brazilian Health Regulatory Agency⁽³⁰⁾ conditional recommendation regard the adoption of strategies to strict glycaemic control in the postoperative phase, besides there is no consensus about how glycaemic level could work as a protective factor for SSI among patients who underwent general surgeries.

Moreover, there have been few investigations evaluating the hyperglycaemia effects or blood glucose control in the postoperative phase of LT recipients^(15, 16, 23, 31). Besides the few studies concerned on the topic among LT recipients^(14-16, 20, 23, 31), the majority of them were observational studies, designed as retrospective cohorts, which could compromise the body's evidence quality^(14, 15, 20, 23, 31). Besides that, in the previous studies enrolled patients underwent liver-kidney transplantation^(14-16, 31), which can cause negative impact on the effects of glycemic control analyses and there is research where recipients presented lower means of Model for End-Stage Liver Disease (MELD) from 19.0 to 28.2^(14-16, 20, 23, 31) that are lower MELD means than the observed in Brazilian transplantation centres. Finally, we observed the absence of clear criteria for SSI diagnosis in some studies^(15, 16, 20, 23).

It is known that the preoperative screening in living donor LT of donors and recipients as baseline characteristics are different of LT whose allografts came from deceased donors; for

instance, liver-kidney recipients who undergo to distinct immunosuppression schemes. Furthermore, lower MELD scores represent LT recipients that could be exposed to diverse risk factors for SSI when compared to LT recipients who the MELD score is higher⁽³²⁾.

Thus, it sounds appropriate that research aiming to evaluate the effect of strict blood glucose control on SSI incidence among LT recipients should be made. In addition, nurse-initiated blood glucose control protocols, among critically ill patients, are frequently developed^(23, 33, 34). And, a recent literature review pointed to the lack of prospective studies that addressed the evaluation of the outcomes of strict glycaemic control among LT recipients on SSI incidence⁽²¹⁾.

The study hypothesis is: the postoperative strict glycaemic control reduces the SSI incidence among LT recipients.

2 RESEARCH OBJECTIVE

To evaluate the effects of a postoperative strict blood glucose control protocol comparatively to an institutional protocol on the SSI incidence among LT recipients.

3 METHODS

The Standard Protocol Items: Recommendations for Interventional Trials (SPIRIT) were used to write this methods chapter⁽³⁵⁾.

It is a randomized open-label clinical trial, in other words, the researchers will not try to blind the patients⁽³⁶⁾. Among the research designs, the randomized clinical trial stands out on the observational designs as a result of the greater capacity to demonstrate causality. It particularly stems from a random allocation process that could remove the possibility of effects observed being explained by differences between the use of co-interventions or by other bias in the outcomes analyses^(37, 38).

This study will be performed by two groups, the first one composed of LT recipients who undergo a standard blood glucose protocol, standardized in the facility selected to conduct this research. That protocol consists in a glucose control according to the result of finger prick test and

subcutaneous injection of regular insulin (BG targeted 130 - 180 mg/dL). The second group will be constituted of patients who undergo a strict blood glucose control (BG target 80 - 130 mg/dL) by a continuous intravenous insulin infusion.

3.1 STUDY SETTING

The study will be conducted in a tertiary referral hospital, service provider for Brazilian Public Health System situated in the countryside of São Paulo State. It is an academic and research hospital licensed by Brazilian Ministry of Health to perform LT since 2009; 40 LT are done each year⁽³⁹⁾.

3.2 ELIGIBILITY CRITERIA

Patients eligible for the trial must be 18 years of age or older, recipients of LT whose allograft came from deceased donors.

The patients that underwent any kind of surgery with or without prosthesis implant in the 30 days before the LT or are submitted to multiple organ transplantation will be excluded from the trial.

3.3 SAMPLE SIZE

Based on previous studies that showed the reduction of any infection incidence among LT recipients the sample size was calculated on the basis of the primary hypothesis^(16, 40). 58 patients are required to have an 80% chance of detecting, as significant at the 5% level, a decrease in the primary outcome measure from 40% in the control group to 10% in the experimental group. Thus, the sample calculation pointed will need 29 patients allocated in each group.

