3.4 SEQUENCE GENERATION AND CONCEALMENT

Participants will be randomly assigned to either standard control or strict control with a 1:1 allocation as a per computer-generated randomisation schedule; the procedure will be performed by an independent statistician.

The randomization schedule will be put into sequentially numbered sealed opaque envelopes by an external expert to research.

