3.16 STATISTICAL ANALYSES PLAN

A Microsoft Excel for Mac 2011® database will be constructed. The data will be typed into two different files to ensure accuracy by an automated check. Afterwards, the data will be transferred to the software Statistical Package for the Social Sciences® for Windows® version 22.0.

The results will be computed with a statistician support, following the research objectives and methods. The following tests will be employed:

- Central tendency and dispersion measures.
- The categorical variables will be analysed by the Pearson's χ^2 test or Fisher's exact test.
- The continuous variables will be analysed by the Student t-test or Mann-Whitney.
- Survival analysis by Kaplan-Meier estimate and Log-rank test.
- Visual inspection of residuals from QQ plot will be used to determine the normality.
- The significant level adopted will be $\alpha=0,05$.

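### The 80% power stated for 29 patients per arm is not delivered by either test the plan names: about 77% under the usual expected-count convention (two-sided test assumed)

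*Protocol*

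**What the plan says.** Section 3.3 of the protocol sets the sample size: "58 patients are required to have an 80% chance of detecting, as significant at the 5% level", for SSI rates of 40% in the control group and 10% in the experimental group, so that "the sample calculation pointed will need 29 patients allocated in each group". It names no formula, test or sidedness, and gives no allowance for loss to follow-up. Section 3.4 plans allocation "with a 1:1 allocation as a per computer-generated randomisation schedule", so 29/29 is the intended split.

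Section 3.10 lists SSI within 30 days as the only primary outcome. For categorical variables, section 3.16 and the SAP carry the same line: "The categorical variables will be analysed by the Pearson's" chi-square test or Fisher's exact test. Neither ties a test to SSI, gives an expected-count threshold, mentions a continuity correction or says whether tests are two-sided. Both set the significance level at 0.05 and stop there.

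**The concern.** A power statement describes one test applied to one design. Section 3.3 gives 80%, while the analysis sections name two tests whose power at 29 per arm could differ from that figure and from each other. If neither reaches 80%, the protocol promises more than its own analysis can deliver, even when the assumed rates are exactly right. The two tests also differ enough in a trial of 58 that the power figure cannot be made exact until the test for SSI is fixed.

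**Working it through.** **Inputs.** Rates 40% and 10%, 29 per arm, 5% level and 80% power (3.3); 1:1 allocation (3.4); Pearson or Fisher (3.16 and SAP). Two assumptions are not in the documents: a two-sided test, and, for the mixed rule below, the common convention of using Fisher when any expected count is below 5.

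**Step 1: reproduce the plan's figure.** Normal approximation, unpooled variance, two-sided 5%:

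n per arm = (1.960 + 0.842)² × (0.4×0.6 + 0.1×0.9) / 0.3² = 7.849 × 0.33 / 0.09 = 28.78, rounded up to 29.

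Power of that formula at 29: 0.3 / √(0.33/29) = 2.812; 2.812 − 1.960 = 0.852; Φ(0.852) = 80.3%. So 58 patients and 80% both reproduce.

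Other variants do not give 29:

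| Formula | n per arm |
|---|---|
| Unpooled, two-sided | 28.78 → 29 |
| Unpooled, one-sided | 22.67 → 23 |
| Arcsine, two-sided | 29.8 → 30 |
| Pooled, two-sided | 32 |
| Pooled with continuity correction, two-sided | 38 |
| Pooled, one-sided | 25 |
| Pooled with continuity correction, one-sided | 32 |

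Two-sided is the only sidedness under which a formula tried here gives 29.

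**Step 2: power of the named tests.** Pearson's statistic uses the pooled variance, which the unpooled formula ignores, and Fisher's test is conservative. I enumerated every pair of SSI counts (0 to 29 in each arm), weighted each by its binomial probabilities at 40% and 10%, and summed the probability of tables with two-sided p ≤ 0.05.

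| Analysis at 29/29 | Exact power | Gap to 80% (points) |
|---|---|---|
| Pearson, uncorrected | 77.8% | 2.2 |
| Pearson, or Fisher if any expected count < 5 | 77.1% | 2.9 |
| Fisher throughout | 68.1% | 11.9 |
| Pearson with continuity correction | 68.1% | 11.9 |

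The mixed rule calls on Fisher in only 4.9% of trials at these rates, which is why it sits close to Pearson.

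**Step 3: sensitivity to the split.** Control/strict, same rates:

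| Split | Pearson | Rule | Fisher |
|---|---|---|---|
| 28/30 | 79.0% | 79.0% | 73.7% |
| 30/28 | 78.2% | 76.6% | 73.3% |
| 27/31 | 78.2% | 77.0% | 73.3% |
| 31/27 | 77.3% | 76.9% | 74.3% |
| 29/28 (57 patients) | 77.9% | 75.5% | 69.6% |
| 26/32 | 81.4% | 79.9% | 74.4% |

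The 68.1% for Fisher is a low point at equal arms. Pearson passes 80% at 26/32, so the shortfall is a statement about the planned 29/29 and nearby splits, not about every possible split.

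**Step 4: how often the choice of test matters.** At 29/29 under the planned rates, Pearson and Fisher fall on opposite sides of 5% in 9.7% of trials. An example is 10 against 3 SSIs: Pearson p = 0.028, Fisher p = 0.056. In 8.9 of those 9.7 points the smallest expected count is at least 5, so the convention selects Pearson. For the four unequal splits of 58 within 27 to 31 per arm, disagreement is 3.0% to 5.3%.

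**The case against.** The strongest reply is that a gap of 2 to 3 points is the ordinary difference between a normal-approximation sample size and exact enumeration, and that the rates matter more. Section 3.3 rests them on studies of any infection, and 40% lies above the SSI range in the Introduction, which "varied from 9.6% to 35.5"%. This is fair as to size, and every power figure here is conditional on 40% against 10%. It does not make 80% true of the planned analysis.

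A second reply is that the hypothesis is directional. A one-sided 5% test at 29/29 would have power of 87.6% (Pearson), 86.4% (rule) and 78.1% (Fisher). The documents do not state sidedness, so this cannot be excluded, but no one-sided formula tried here leads to 29.

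A reader might also infer more than the documents support:

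- That 58 is a miscalculation. It is not; a standard formula gives it. That this formula was the one used is an inference, since 3.3 names none.
- That the trial has only 68% power. Nothing says Fisher or a continuity correction will be used throughout.
- That the result can be steered by choosing the test afterwards, the more so because "It is a randomized open-label clinical trial". Open-label treatment has no bearing on which 2×2 test is chosen, the abstract provides for blinded adjudication of SSI, and the usual convention already settles most of the disagreement. The unstated rule is a missing detail.

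**Conclusion.** The point holds in a limited form. Assuming a two-sided 5% test and the planned rates, neither named test delivers 80% at 29/29: power is 77.8% with Pearson and 77.1% under the usual expected-count convention. The shortfall is small on that reading and reaches about 12 points only with Fisher throughout or a continuity correction. The sentence in 3.3 is therefore wrong as a description of the planned analysis, though the sample size behind it is not an arithmetic error.

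The missing selection rule is a secondary clarification. It is limited to the text that could be read, because part of the SAP was not in the copy examined; the protocol's own section 3.16 contains no such rule.

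**What to change.** 1. In 3.3, replace the 80% statement with: *about 77% power (two-sided 5%, 40% vs 10%, 29 per arm analysed, before any loss to follow-up or interim adjustment)*. Name the test to which this figure applies and the formula that gave 29.
2. In 3.16 and the SAP, so that the figure describes the actual analysis, add: *SSI within 30 days will be compared between groups with a two-sided 5% test: Pearson's chi-square without continuity correction, or Fisher's exact test if any expected count is below 5.* The words on continuity correction matter, because applying it lowers power at 29/29 to 68.1%.

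**Cost.** A few sentences, no extra patients and no test the plan does not already name. The stated power becomes slightly less favourable. The rule's maximum type I error is 4.8% at 29/29 but can slightly exceed 5% with unequal arms: 6.3% at 28/29 (at a true rate of 50% in both arms) and 5.3% at 27/31 or 31/27. At common rates within the Introduction's range, it is at most 4.7% at 29/29 and 5.4% at 28/29.

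If the sponsor prefers to keep 80%, 31 per arm (62 patients) gives 80.9% under the rule, and Fisher throughout would need 36 per arm (80.0%). Neither is necessary to correct the statement.

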3.4 SEQUENCE GENERATION AND CONCEALMENT

Participants will be randomly assigned to either standard control or strict control with a 1:1 allocation as a per computer-generated randomisation schedule; the procedure will be performed by an independent statistician.

The randomization schedule will be put into sequentially numbered sealed opaque envelopes by an external expert to research.

3.5 RECRUITMENT

All the candidates for LT or representatives, during the ambulatory pre-transplant evaluation in the facility selected to conduct the study, will be contacted by the to check the inclusion and exclusion criteria, as well to explain the possible risks and the benefits of participating in research following the consent form will be signed.

3.6 ALLOCATION

After the patients' acceptance in participating in the research, in the ICU admission, any bedside blood glucose reading equal or superior to 130 mg/dL in the first 24 hours of the postoperative period will determine the LT recipient's allocation in the study. The sealed opaque envelope will be opened by an independent Registered Nurse to allocate the participant in the standard blood glucose control group or strict blood glucose control group.

3.7 INTERVENTIONS

To implement the protocols of glycaemic control, the researcher has established, in an earlier study, a previous relationship with the surgeons and intensive care doctors⁽¹³⁾. Consequently, there will be for each LT recipient a medical order of the randomised intervention.

3.7.1 STRICT GLYCEMIC CONTROL GROUP

The strict protocol adopted to conduct the study was proposed by Keegan e Cols.⁽²³⁾ (2010) to be used among adult LT recipients that consists of a continuous intravenous insulin infusion. The targeted blood glucose range is 80-130 mg/dL. The procedure must be stopped when the patient can ingest at least 50% of liquid diet or receive bolus tube feedings (Appendix A).

3.8 STANDARD GLYCEMIC CONTROL GROUP

The control group will be submitted to the standard (targeted BG: 130-180 mg/dL) institutional blood glucose control that is an escalating subcutaneous insulin dose for a given blood glucose reading, as follows:

Figure 1 - Subcutaneous insulin scheme. São Paulo, 2017.

Blood glucose reading	Subcutaneous human regular insulin dose
≤ 180 mg/dL	-
≥ 181 mg/dL and ≤ 250 mg/dL	5 IU*
≥ 251 mg/dL and ≤ 300 mg/dL	10 IU*
≥ 301 mg/dL	15 IU*

* UI: International Unity.

Source: Facility selected to conduct the study.

3.9 THE BLOOD GLUCOSE MEASURE

As an institution routine, either the standard group and the strict group will be submitted to a finger prick test each hour by nursing staff, trained by the researcher, under the supervision of a Registered Nurse employing a bedside glucose meter (FreeStyle Precision Pro® Abbott) calibrated following the manufacturer advice.

3.10 PRIMARY OUTCOME

Surgical site infection following the Centers for Disease Control and Prevention defining criteria:

SSI occurs within 30 or 90 days after the operation and involves skin or subcutaneous tissue of the incision, deep soft tissues or organ and spaces, which were opened or manipulated during an operation⁽¹⁾.

LT does not involve the presence of implants left in place thereby the period for detecting SSI is within 30 days after the operation, where day 1 = the procedure date⁽¹⁾.

3.11 SECONDARY OUTCOMES

The frequency of variables between both groups will be analysed as follows:

- Hyperglycaemia > 250 mg/dL⁽²³⁾;
- Hypoglycaemia < 60 mg/dL⁽²³⁾;
- Time for SSI development;
- Time of mechanical ventilation through ICU stay;
- ICU stay;

- Postoperative ward stay;
- Death within 90 days after LT.

3.12 EVALUATION OF PRIMARY OUTCOME

3.12.1 Through hospital stay

The researcher will evaluate the surgical wound on alternate days before the dressing changes and patient's bathing.

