3.12.2 The period following the hospital discharge until the 30th postoperative day

The researcher will contact the liver transplant recipient on alternate days by telephone to detect any signs and symptoms of SSI. Also, the surgical wound will be evaluated every 7 days during the ambulatory doctor's assessment.

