3.12.3 Evaluation of surgical wound during the hospital stay and after discharge

Facing a suspected SSI case, given the CDC criteria fulfilment, immediately the researcher will communicate with the healthcare team and proceed to register in the nursing records.

After that, the researcher will take a picture of the surgical site, using a digital camera designated for this activity. The clinical records and image will be sent to the adjudication committee for evaluation.

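### Organ/space SSI is part of the primary outcome, but the in-hospital plan schedules only wound evaluation, so these infections may be under-ascertained, possibly differently by arm

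*Protocol*

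**What the plan says.** Protocol 3.10 adopts the CDC definition. An SSI is an infection that "involves skin or subcutaneous tissue of the incision, deep soft tissues or organ and spaces, which were opened or manipulated during an operation". The window is also fixed there: "the period for detecting SSI is within 30 days after the operation, where day 1 = the procedure date".

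Detection is described in 3.12, in three parts:

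- **In hospital (3.12.1).** The section is one sentence, which begins "The researcher will evaluate the surgical wound on alternate days before the dressing changes" and adds no other detection step.
- **After discharge (3.12.2).** The researcher contacts the recipient "on alternate days by telephone to detect any signs and symptoms of SSI", and "the surgical wound will be evaluated every 7 days during the ambulatory doctor's assessment".
- **Once a case is suspected (3.12.3).** If the CDC criteria are fulfilled, the researcher informs the healthcare team and makes a nursing record. Then "the researcher will take a picture of the surgical site", and the image goes to the committee together with the clinical records.

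Under 3.13, three experts classify each referred case by the CDC criteria and simple majority. The Abstract calls this committee blinded. Section 3 calls the trial open-label. The statistical analyses plan (Protocol 3.16 and SAP) lists tests and does not deal with ascertainment.

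**The concern.** The definition reaches organs and spaces, but the only scheduled in-hospital activity is directed at the incision. No step has the researcher look at cultures, imaging, drain findings or reoperation reports during the stay. An intra-abdominal infection under a clean incision would enter the trial only if someone happened to bring it to the researcher's notice.

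Two things are at stake:

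- **Lost events.** Missing the same share of cases in both arms lowers both rates, shrinks the absolute difference and costs power in a trial of 58 patients.
- **Detection that depends on arm.** The allocated treatment is visible at the bedside, since one arm receives a continuous intravenous infusion and the other subcutaneous injections. Cases that surface informally do so through people who know the arm. If that differs between arms, the result is bias as well as lost power.

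Time to SSI, a secondary outcome in 3.11, depends on the same detection.

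**Working it through.** **1. Is there an in-hospital route for organ/space SSI?** Setting the sections side by side:

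| Step | When | What it looks at | Can it find an organ/space case with a clean wound? |
|---|---|---|---|
| Wound evaluation, 3.12.1 | In hospital, alternate days | Incision | Not by itself |
| Telephone call, 3.12.2 | After discharge, alternate days | Any signs and symptoms | Possibly, but only after discharge |
| Wound evaluation, 3.12.2 | After discharge, every 7 days | Incision | Not by itself |
| Photograph and clinical records, 3.12.3 | After suspicion | Site image and records | Helps classify a case, does not find it |
| Committee, 3.13 | After referral | What it is sent | No, it sees only referred cases |

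No row gives a scheduled in-hospital step that would find such a case.

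**2. Reproducing the stated sample size.** The inputs from Protocol 3.3 are 40% in the control group, 10% in the experimental group, 80% power, a 5% level and 29 per arm. Allocation is 1:1 (3.4). Sidedness is not stated, so two-sided is assumed. With the unpooled normal approximation,

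n per arm = (1.960 + 0.842)² × [0.40×0.60 + 0.10×0.90] / (0.40 − 0.10)² = 7.85 × 0.33 / 0.09 = 28.8, which rounds up to 29 per arm and 58 in total.

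This matches the protocol, so the point does not dispute the sample-size arithmetic.

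**3. Illustration of equal under-ascertainment.** Assume that a share q of all SSI goes undetected, the same in both arms, and that 40% and 10% are the rates under full ascertainment. The observed rates become 0.40(1 − q) and 0.10(1 − q). Power is Φ(d / √(v/29) − 1.960), where d is the difference and v = p₁(1 − p₁) + p₂(1 − p₂).

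| q | Rates | d | v | d/√(v/29) | Power, unpooled normal | Power, exact for Pearson test | n per arm for 80% (7.85·v/d²) |
|---|---|---|---|---|---|---|---|
| 0 | 40% vs 10% | 0.30 | 0.3300 | 2.81 | 80.3% | 77.8% | 29 |
| 10% | 36% vs 9% | 0.27 | 0.3123 | 2.60 | 74.0% | 71.7% | 34 |
| 20% | 32% vs 8% | 0.24 | 0.2912 | 2.39 | 66.8% | 65.2% | 40 |
| 30% | 28% vs 7% | 0.21 | 0.2667 | 2.19 | 59.1% | 58.5% | 48 |

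The exact column sums binomial probabilities over all tables in which the uncorrected Pearson test is significant. The relative risk is 0.10/0.40 = 0.25 in every row, because (1 − q) cancels.

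**4. Unequal under-ascertainment.** If q differs by arm, (1 − q) no longer cancels and the relative risk shifts. The documents give no basis for a value, so none is put on it here.

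**The case against.** The strongest reply is that the protocol is short, not restrictive. Section 3.12.3 does not limit where suspicion may come from. Its condition is fulfilment of the CDC criteria, which for organ/space infection are not confined to wound appearance. Clinical records go to the committee with the image. The researcher has an established relationship with the surgeons and intensive care doctors (3.7), clinical diagnosis continues independently of adjudication (3.13), and recipient records are already a data source for donor variables (3.15).

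Much of this stands, and it rules out three stronger readings that a reader might infer:

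- *That surveillance consists of inspecting and photographing the wound.* The photograph follows suspicion and is not a surveillance tool, and the records go with it.
- *That organ/space infections in hospital never raise a suspicion.* The text leaves other sources of suspicion open, so it cannot be said that these cases will be missed.
- *That the trial does not measure the outcome it defines, or measures incisional SSI only.* Incisional cases are covered, organ/space cases can be referred, and the post-discharge calls are not limited to the wound.

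The reply does not supply a procedure. Records sent after suspicion cannot reveal a case that nobody suspected, and the CDC criteria are a standard for judging a case, not a schedule for finding one.

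The objection to the size also stands in part. Section 3.3 takes its rates from studies of any infection, and the Introduction gives SSI incidence of 9.6% to 35.5%. It is therefore unclear what level of ascertainment the 40% reflects. The power loss is not measured from a known baseline.

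**Conclusion.** The concern holds as a gap in ascertainment. The plan includes organ/space SSI in the primary outcome but states no systematic way to detect it during the hospital stay. These infections may be under-ascertained, and in an open-label trial the cases that do come to notice may differ by arm. Blinded adjudication protects the classification of referred cases only.

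The power figures (from 80% to between 74% and 59% by the unpooled approximation, or from 78% to between 72% and 58% for the exact Pearson calculation) are illustrations. They rest on an assumed missed share of 10% to 30%, equal missing in both arms, a two-sided test, and the protocol's 40% and 10% as fully ascertained rates. Under equal missing the relative risk is not biased. Unequal missing is potentially the more serious possibility, but it cannot be sized from the documents. The change is worth making because it is cheap, not because a failure has been shown.

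**What to change.** In 3.12.1, add to each alternate-day assessment a short checklist review by the same researcher of records that already exist, read against the CDC organ/space criteria: cultures, imaging already done, drain or aspirate findings, and reoperation reports. In 3.12.2, add one closing review of the same items at day 30. Apply both to every participant, identically in the two arms. State in 3.12.3 that any positive item is referred to the committee even when the wound is clean and there is nothing to photograph.

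The cost is a few minutes per visit at assessments already planned, plus the day-30 check. No new tests or extra staff are needed, and care is unaffected because 3.13 already separates adjudication from treatment. The downside is more cases for the committee to classify. One limit remains: a review of existing records standardises what the researcher looks at, but not which investigations an unblinded clinical team orders.
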